The objectives of this proposal, accordingly, are to corroborate data from our preliminary human studies showing that a high protein diet results in body weight loss. We will correlate the observed clinical findings with an understanding of normal and pathological appetite regulatory mechanisms in experimental animals. In order to accomplish the stated goals of this program, we have brought together interdisciplinary collaborations at our VA Medical Center from diverse backgrounds including: microbiome, cell biology, molecular biology, neurophysiology and human clinical investigations, including health services research to investigate the mechanisms regulating feeding behavior and obesity. Our proposal is focused on addressing three hypotheses linking clinical and translational approaches that are critical to understanding the pathophysiology of satiety/obesity.

1. A higher protein replacement diet will result in early satiety signaling and weight loss in obese patients and a differential pattern of postprandial GI hormone release.
2. Patients on the high protein diet will have shifts in the composition and function of their intestinal microbiome.
3. Abundance of specific fecal microbes can be used to predict response to a high protein diet.

C. Specific Objectives.

AIM 1: To Confirm the Hypothesis that a High Protein Diet Reduces Body Weight and Alters the Pattern of Postprandial Gut Hormone Release in Obese Patients.

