Study design: This is a randomized study using the same subjects described in Aim 1. Nutritional assessment, physical examination, bioelectrical impedance, laboratories will be performed at baseline, and weeks 2, 4, 6, 8, 12 and 16. Stool samples will be collected on day 3, 7, 14, 17, 21, 28, 42, 56, 84 and 112.

Study timeline: Data collection will be completed at week 16. The stool samples collected during the study period will be used for 16S rRNA sequencing, shotgun metagenomics, and data analysis.

Bioinformatics protocol: Patient characteristics (physical measurements, lean body mass, laboratories, demographic traits) at baseline will be compared using a 2-sided t-test (for numerical variables) or chi-square test (for categorical variables) to evaluate the randomization. 3DFR and FFQ performed at each timepoint will be used to assess the predicted protein content of the patient's diet compared to baseline to evaluate the success of the dietary intervention. Clinical response endpoints significantly associated with HPD in Aim 1 will then be correlated with the abundance of microbes found to be enriched or depleted on a HPD in Aim 2.1. These endpoints will be fitted to multivariate models to adjust for baseline clinical covariates including BMI, age, sex, and smoking status. Spearman correlations will then be calculated for all combinations of residuals for the clinical endpoints and for microbial abundance (using DESeq2 fitted multivariate models from Aim 2.1 to adjust for covariates). Separate correlation analyses will be performed at baseline and each of the time points during treatment.

Microbes that are independently associated with clinical response to a HPD will then be used to create random forests classifiers to predict response. Subjects in the HPD group will be identified as responders if they had a decrease in any of the clinical endpoints that exceeded the predictions of the multivariate model for the NPD group. The sensitivity and specificity of the classifiers will be estimated using 10-fold cross-validation. Classifiers constructed from baseline microbial abundance and microbial data at each time point will be compared to determine the earliest time point when accurate predictions of response are possible.

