The above analytic pipeline will then be applied to the shotgun metagenomics data obtained at baseline and day 112. Gene families and/or metabolic pathways that shift in response to a HPD may be more consistent across diverse populations than abundance of specific microbes such as *Akkermansia* which could vary greatly from person to person⁽⁷⁸⁾. The performance of classifiers constructed from metagenes will be compared to those built from microbial abundance to identify the approach that is most predictive for response.

Expected results/potential pitfalls: We predict that a subset of the HPD-associated microbes and metagenes will be associated with response in the HPD. We also expect that baseline and/or post-dietary intervention abundances of microbial features can be used to generate accurate random forests predictors for clinical response. We used similar bioinformatics approaches to identify the inverse correlation of *Akkermansia muciniphila* with body fat in our rodent model and to predict IBD status in families with pediatric inflammatory bowel disease. Accordingly, we do not anticipate problems performing these analyses.

Human Subjects

1. Risk to Subjects

(a) Human Subjects Involvement and Characteristics:

Approximately 198 healthy volunteers age 30 years and older between BMI of 27 to 40 kg/m² will be able to take part in this study. Pregnant women or women likely to become pregnant during the course of the study may not participate in this study. Female subjects must not be

able to conceive by reason of surgery, radiation, 1 year past the onset of menopause, or an approved method of contraception. No vulnerable subjects will be included in the study. (See the detail in the Research Plan, Proposed Work, Aim 1, Sections of Recruitment, Procedures, and Statistical Analysis)

(b) **Sources of Materials:** See the detail in the Research Plan, Proposed Work, Aim 1, Section of Procedures.

(c) **Potential Risks:**

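### Aim 3 names the earliest accurate time point among 11 classifiers, and the better of two data types, with no benchmark against chance and no allowance for the search

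*Combined protocol and SAP*

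**What the plan says.** Section 1.B lists as its third hypothesis: "Abundance of specific fecal microbes can be used to predict response to a high protein diet". Section 4.C (Aim 3, Bioinformatics protocol) says how this will be examined. Microbes associated with clinical response feed random forest classifiers within the high-protein group. Their performance is assessed as follows: "The sensitivity and specificity of the classifiers will be estimated using 10-fold cross-validation".

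The sampling plan reads "Stool samples will be collected on day 3, 7, 14, 17, 21, 28, 42, 56, 84 and 112", which is ten days. Aim 3 also plans a baseline classifier: "Classifiers constructed from baseline microbial abundance and microbial data at each time point". The stool-day list omits baseline, but the week 0 assessments in section 4.A include stool collection. The 16S classifiers "will be compared to determine the earliest time point when accurate predictions of response are possible".

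The same steps are then repeated on a second data type: "The above analytic pipeline will then be applied to the shotgun metagenomics data obtained at baseline and day 112". Metagene classifiers "will be compared to those built from microbial abundance to identify the approach that is most predictive for response".

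Neither Aim 3 nor any other section says what level of sensitivity, specificity or AUC counts as accurate. None plans a test against chance, a held-out sample or an interval for classifier performance. The multiplicity adjustment in Aim 2.1 covers the differential-abundance tests. The two-sided 0.05 level in the Aim 1 statistical section sets no bar for a classifier.

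**The concern.** Cross-validated accuracy from about 80 subjects is noisy. When 11 such estimates are inspected and the first one that looks good is reported, the search itself can produce an apparently predictive time point. Because the bar is not fixed in advance, it can be settled after the estimates are known.

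The answer to the third hypothesis is at stake: a statement that stool microbes predict response from a given day, which later work would build on. Choosing between 16S and metagenes has a related weakness, since one estimate will almost always exceed the other and no rule says when the gap is more than noise.

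**Working it through.** **Inputs from the protocol**
- 100 subjects per arm (4.A, Study Design) and 20% dropout: 100 × (1 − 0.20) = 80. This reproduces the figure of about 80 per group in Aim 2.1.
- 16S classifiers: 10 stool days + baseline = 11. Metagene classifiers: 2. Total 13.

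**Assumptions, not in the protocol**
- AUC cut-offs, number of candidate microbes, correlation between repeat samples, and responder share.
- A responder improves on any carried-forward endpoint. With independent, symmetric endpoints the null share is 50%, 75% or 87.5% for one, two or three endpoints, so 40/40, 60/20 or 70/10 of 80 subjects.

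**Step 1, formula.** The null standard error of an AUC is √[(n1+n2+1)/(12·n1·n2)]. For 40/40 it is √(81/19,200) = 0.065. Then P(AUC ≥ 0.60) = P(Z ≥ 0.10/0.065) = 0.062, and over 11 independent looks 1 − (1 − 0.062)^11 ≈ 0.50.

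| Responders/non-responders | SE | Any of 11 ≥ 0.60, independent | Same, AUC correlation 0.5 | Any of 11 ≥ 0.70, independent |
|---|---|---|---|---|
| 40/40 | 0.065 | 50% | 30% | 1% |
| 60/20 | 0.075 | 65% | 40% | 4% |
| 70/10 | 0.098 | 84% | 55% | 21% |

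**Step 2, simulation without feature selection.** Set-up: 80 subjects split 40/40, 20 pure-noise microbes, within-subject feature correlation 0.5, random forest with 10-fold cross-validation, 11 time points. It was run twice.

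| Some time point reaches | 140 trials | 120 trials |
|---|---|---|
| AUC 0.55 | 94% | 96% |
| AUC 0.60 | 66% | 65% |
| AUC 0.65 | 26% | 25% |
| AUC 0.70 | not tabulated (95th percentile of best AUC 0.69) | 5% |
| Mean of sensitivity and specificity 0.60 | 54% | 58% |

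A single time point reached 0.60 in 10% of cases. As a check, 1 − 0.90^11 = 0.69, close to 65–66%. The mean AUC was 0.496, so each estimate is unbiased; the best of 11 averaged 0.62. Monte Carlo error on 65% is √(0.65 × 0.35/120) = 0.044, about ±9 points. These rates exceed the 30% in Step 1 because refitting in folds raised the SD of the AUC to about 0.08, and AUCs at different time points correlated at only 0.08 although the features correlated at 0.5.

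**Step 3, adding microbe selection.** Set-up: 100 noise microbes selected at Spearman p < 0.05, 40/40, 21 replicates (imprecise).
- Selected on all subjects before cross-validation: mean null AUC 0.65; some time point ≥ 0.60 in 100% of replicates and ≥ 0.70 in 86%.
- Selected inside the training folds: mean null AUC 0.50; 71% and 19%.

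In-fold selection removes the bias but not the search.

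**Step 4, if each classifier were tested at 5%.** 1 − 0.95^11 = 43.1% for independent time points, falling to 26%, 19% and 12% at correlation 0.5, 0.7 and 0.9. For all 13 classifiers, 1 − 0.95^13 = 48.7%. The protocol contains no such test. Bonferroni control at 0.05/11 = 0.00455 (z = 2.61) would need an AUC of about 0.50 + 2.61 × 0.065 = 0.67 with 40/40, 0.70 with 60/20 and 0.76 with 70/10.

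**Step 5, what must be permuted.** Microbes are selected by correlation with endpoint residuals, not with the responder label. In 40 null replicates, permuting labels alone still declared a predictive time point in 95%. Permuting endpoint values and labels together gave the correct null: mean best AUC 0.76 in both actual and permuted data.

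**The case against.** A defence has four parts.

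- **The rule is a threshold.** Seeking the earliest accurate time point means that no time point may qualify. This stands. At an AUC bar of 0.70 the null rate without feature selection is only about 5%. A reader might infer that the plan would usually find a false predictor. The documents do not support that, because they give no bar: it holds at about 0.60 or below and fails at 0.65. On the scale that the protocol uses, sensitivity and specificity, 54% of 140 trials (95% interval about 46–62%) cannot be told apart from half.
- **There are screens upstream.** Only endpoints significant in Aim 1 and microbes differing by diet in Aim 2.1 go forward, then only microbes associated with response. If none qualifies, no classifier is built. Had the Aim 3 correlations been Benjamini–Hochberg adjusted, some noise microbe would pass in about 42% of null trials (adjusting within time point) or 6% (pooled). The protocol states no such adjustment. The first two screens test diet effects, so both can open while prediction within the high-protein group is still null. The Step 2 simulation describes that situation but omits the microbe selection, so its rates are not those of the full pipeline.
- **The data-type choice is not a search over 11 points.** This stands. Shotgun data exist only at baseline and day 112, and naming the higher of two estimates does not by itself support the third hypothesis.
- **The aim is secondary.** This also stands, and it limits the severity. It does not remove the need for a benchmark.

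**Conclusion.** The gap is real and no other section fills it: there is no chance benchmark, no accuracy bar and no control over 11 time points (13 classifiers in all). Its size depends on the missing bar. Under no signal, with no feature selection and an even responder split, the false-positive chance runs from about 65% (AUC 0.60) through 25% (0.65) to 5% (0.70). Selecting microbes on all subjects before cross-validation raises it sharply. The text reads that way but does not say so outright, so this is a likely reading and not an established fact.

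All rates rest on assumed responder balance, number of microbes and correlation. The lack of a benchmark does not depend on those assumptions. The change should be made before Aim 3 is analysed. The primary weight-loss comparison is untouched.

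**What to change.** Amend the Aim 3 Bioinformatics protocol as follows.

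1. Carry out the microbe selection inside each cross-validation training fold.
2. Add a permutation benchmark. At least 1,000 times, permute each high-protein subject's whole clinical outcome record (endpoint values or residuals together with the responder label) against the microbiome data. Rerun the full pipeline at all time points and record the maximum cross-validated AUC. Permuting the label alone is not enough (Step 5).
3. Call a time point predictive only if its AUC exceeds the 95th percentile of that maximum, and state that none is a possible result. This uses the actual dependence between time points, so no correlation has to be assumed.
4. Compare 16S with metagenes only at baseline and day 112. Report the AUC difference with a 95% interval from subject-level resampling that keeps copies of a subject in the same fold. Name a better approach only if the interval excludes 0.

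The cost is computing time and a short addition to the text, with no new subjects or samples. The bar is stricter, so a weak true predictor is less likely to be declared.
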